8.6. Electronic Columbia Suicide Severity Rating Scale

The eC-SSRS Baseline/Screening version will be completed at visit 1, and the eC-SSRS Since Last Visit version will be completed at all other visits (visits 2, 3, 4, and 5), including unscheduled visits. Any positive findings on the eC-SSRS Since Last Visit version require evaluation by a physician or doctoral-level psychologist.

Data for patients with positive findings (having suicidal ideation or suicidal behavior) will be listed.

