## **7.9. Assessment of Suicidality**

The study population being administered fremanezumab should be monitored appropriately and observed closely for suicidal ideation and behavior or any other unusual changes in behavior. Consideration should be given to discontinuing fremanezumab in participants who experience signs of suicidal ideation or behavior.

Families and caregivers of participants being treated with fremanezumab should be instructed to monitor participants for the emergence of unusual changes in behavior, as well as the emergence of suicidal ideation and behavior, and to report such symptoms immediately to the study investigator.

The eC-SSRS will be used to assess the patient's suicidal ideation (severity and intensity) and behavior ([Posner et al 2011](#)). The eC-SSRS Baseline/Screening version will be completed by the patient at visit 1, and the eC-SSRS Since Last Visit version will be completed by the patient at every visit thereafter, including unscheduled visits. Any positive findings on the eC-SSRS Since Last Visit version requires evaluation by a physician or doctoral-level psychologist.

A positive finding will be defined as a current suicide ideation with some intent to act and no plan. The investigator, based on his medical judgment, will determine if the patient should be

seen by a mental health specialist and if he/she should continue participating in the study. If a patient reports current suicide ideation with specific plan and intent, then the patient should be immediately discontinued from the study and seen by a mental health specialist.

Any patient should be excluded if any suicidal behaviors are reported.

Any patient with lifetime behaviors (actual, interrupted, and aborted attempts and preparatory actions) should be excluded and/or discontinued from the study.

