### **9.7. Safety Analysis**

Safety analyses will be performed on the safety analysis set (Section 9.2.2). Safety assessments and time points are provided in Table 2.

All adverse events will be coded using the Medical Dictionary for Regulatory Activities. Each patient will be counted only once in each preferred term or system organ class category for the

analyses of safety. Summaries will be presented for all adverse events (overall and by severity), adverse events determined by the investigator to be related to test IMP (defined as related or with missing relationship) (overall and by severity), serious adverse events, and adverse events causing withdrawal from the study. Patient listings of serious adverse events and adverse events leading to withdrawal will be presented.

The use of concomitant medications will be summarized by therapeutic class using descriptive statistics. Concomitant medications will include all medications taken while the patient is treated with IMP.

Changes in laboratory, ECG, and vital signs measurement data will be summarized descriptively. All values will be compared with prespecified boundaries to identify potentially clinically significant changes or values, and such values will be listed.

Safety data will be summarized descriptively overall and by treatment group. For continuous variables, descriptive statistics (n, mean, SD, median, minimum, and maximum) will be provided for actual values and changes from baseline to each time point. For categorical variables, patient counts and percentages will be provided. Descriptive summaries of serious adverse events, patient withdrawals due to adverse events, and potentially clinically significant abnormal values (clinical laboratory or vital signs) based on predefined criteria will also be provided.

If any patient dies during the study, a listing of deaths will be provided, and all relevant information will be discussed in the patient narrative included in the clinical study report.

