1.3. Safety Endpoints

The safety endpoints are as follows:

- occurrence of adverse events throughout the study
- clinical laboratory (serum chemistry, hematology, coagulation, and urinalysis) test results at each visit
- vital signs (systolic and diastolic blood pressure, oral temperature, and pulse rate) measurements at each visit. Note: Oxygen saturation will be measured in cases of suspected anaphylaxis and severe hypersensitivity. Respiratory rate will also be measured in these cases but not as a standard vital sign.
- 12-lead electrocardiogram (ECG) findings at screening, baseline, and week 12

- use of concomitant medication during the study
- clinically significant changes in physical examinations, including body weight
- injection site reaction (ie, erythema, induration, and ecchymosis) and injection site pain assessments
- occurrence of hypersensitivity/anaphylaxis reactions
- suicidal ideation and behavior as measured by the electronic Columbia Suicide Severity Rating Scale (eC-SSRS)

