8. SAFETY ANALYSIS

8.1. General

The safety analysis set will be used for all safety analyses. Summaries will be presented using descriptive statistics by treatment group and all fremanezumab as actually received unless otherwise stated.

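### SAP 8.6 plans only a listing of eC-SSRS positives, so post-dose suicidal ideation and behaviour on this scale has no by-arm summary

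*SAP*

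**What the plan says.** SAP 1.3 lists "suicidal ideation and behavior as measured by the electronic Columbia Suicide Severity Rating Scale" among the safety endpoints, and Protocol 2.1 has it as a secondary safety endpoint. SAP 8.6 sets the schedule: "The eC-SSRS Baseline/Screening version will be completed at visit 1, and the eC-SSRS Since Last Visit version will be completed at all other visits", with unscheduled visits included. It then states a single output: "Data for patients with positive findings (having suicidal ideation or suicidal behavior) will be listed". It plans no count, percentage, shift table or comparison by arm.

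Two general rules bear on this. Protocol 9.7 says safety data are described overall and by treatment group, and adds: "For categorical variables, patient counts and percentages will be provided". SAP 8.1 says: "Summaries will be presented using descriptive statistics by treatment group and all fremanezumab as actually received unless otherwise stated". The SAP Introduction gives the SAP precedence where the two documents differ and leaves differences to be explained in the study report. SAP Section 17 records none.

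The documents also give two meanings to the term positive. SAP 8.6 applies it to any ideation or behaviour. Protocol 7.9 says: "A positive finding will be defined as a current suicide ideation with some intent to act and no plan".

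**The concern.** A named endpoint, measured on every patient at every visit, ends in a list of individuals. A list does not show how many patients per arm had a finding after dosing, or out of how many, unless the reader counts by hand. The SAP does not say that the list will carry the columns needed for that count.

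At stake is a descriptive safety statement: the number and percentage of patients in each fremanezumab arm and on placebo with ideation or behaviour first seen after dosing. Protocol 3.4, 4.3 and 7.9 treat such findings as relevant to whether a patient continues on drug, so a reader of the study report would expect a group-level count.

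A second, separate problem is that one term has two meanings while both documents attach the same clinical evaluation to it.

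**Working it through.** There is no stated figure to reproduce for this endpoint, so most of the check is a comparison of passages.

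1. **Is there a by-arm eC-SSRS summary anywhere?** SAP 8.6 plans a listing only. SAP 8.1 governs how summaries are laid out where a section plans them, and 8.6 plans none. Other SAP safety sections do plan summaries: suspected anaphylaxis (8.5), laboratory values with shifts (8.8), vital signs (8.10) and ECG findings with shifts (8.11).

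2. **Do the adverse event tables fill the gap?** In part. SAP 8.3 summarises treatment-emergent adverse events, and under 8.1 this is by treatment group. Suicidality reported as an adverse event would appear there. The question is whether an eC-SSRS positive must be so reported. The protocol sends clinically significant laboratory (7.4), physical examination (7.5), vital sign (7.6) and ECG (7.7) findings to adverse event recording, and injection-site reactions too (7.11). Protocol 7.9 has no such instruction for the eC-SSRS.

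3. **Is the listing limited to post-dose assessments?** No limit is stated. Visit 1 uses the Baseline/Screening version. Protocol Appendix B places the visit 2 eC-SSRS among the procedures before dosing. By contrast, SAP 8.8 and 8.10 limit abnormal laboratory and vital sign values to postbaseline data, and 8.3 limits adverse event summaries to events at or after the first dose.

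4. **Which pre-dose findings could appear?** Exclusion g removes past suicide attempts and current active ideation. Protocol 7.9 removes lifetime suicidal behaviours, including preparatory acts. What remains is mainly passive or past ideation.

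5. **Do the two meanings conflict?** SAP 8.6 and Protocol 7.9 both require evaluation by a physician or doctoral-level psychologist for any positive finding on the Since Last Visit version. Ideation without intent is positive in SAP 8.6 but not under the definition in Protocol 7.9. Every patient positive under 7.9 also meets the wider SAP meaning, so none would be lost from the listing.

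6. **How precise would a by-arm table be?** Assume all planned patients are treated: 300/3 = 100 per arm and 200 on fremanezumab. For zero events the exact (Clopper-Pearson) 95% upper limit is 1 − 0.025^(1/n).
   - n = 100: 1 − 0.025^(1/100) = 3.6%
   - n = 200: 1 − 0.025^(1/200) = 1.8%
   - 3 events in 100 (an illustrative count): 3.0%, exact 95% interval 0.6% to 8.5%

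**The case against.** The strongest reply is that suicidality is not left without a by-arm result. Events reported as adverse events, including serious ones and those causing withdrawal, are tabulated by arm. This stands against the wider inference a reader might draw, that the trial gives no by-arm result for suicidal ideation or behaviour; the documents do not support that. It does not cover the scale-based endpoint, because nothing makes an eC-SSRS positive an adverse event.

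Second, Protocol 9.7 is a general convention. It names adverse events, medications, laboratory, ECG and vital sign data but not the eC-SSRS, and SAP 8.1 allows exceptions. That is fair, and it makes the departure modest. Still, eC-SSRS findings are safety data, 8.6 gives no reason for departing from the rule, and Section 17 declares no change.

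Third, the sentence just before the listing in 8.6 concerns the Since Last Visit version, so visit 1 may be outside the listing. That reading is possible, but visit 2 uses the same version and comes before dosing. A reader might also infer that the plan deliberately includes pre-dose positives, or that they would dominate the listing. The text supports only that they are not excluded, eligibility narrows them, and the documents give no rates from which to estimate a share.

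Fourth, an action threshold for sites need not equal a reporting filter. True in general, but SAP 8.6 uses one term for both jobs in consecutive sentences.

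Fifth, about 100 patients per arm can say little about a rare outcome. That limits interpretation of the counts; it is not a reason to leave them out.

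**Conclusion.** The point holds in this form: the SAP plans no by-arm summary of post-dose eC-SSRS ideation or behaviour, although this is a named safety endpoint and the protocol's general rule calls for counts and percentages by treatment group. The adverse event tables are a partial route, not an assured one. The listing does not exclude pre-dose findings.

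The size is one missing descriptive table. No efficacy result, sample size or error rate is affected. The precision figures assume about 100 treated patients per arm and show that the table would describe the arms rather than test a difference between them.

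The two meanings of positive finding are a separate inconsistency. A reader might infer that they cause the missing summary; they do not, since 8.6 would plan only a listing under either meaning. This review takes no view on which definition is right.

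**What to change.** - **Table.** In SAP 8.6, add a table on the safety analysis set, by arm and for all fremanezumab, giving the number and percentage of patients with any post-dose suicidal ideation and with any post-dose suicidal behaviour. Use visits 3 to 5 (including early withdrawal) and unscheduled visits after the first dose.
- **Treatment-emergent row.** Add a row for patients who had no such finding at visits 1 and 2.
- **Listing.** Keep it, and flag each record by arm, visit and pre-dose or post-dose.
- **Interpretation.** State that the counts are expected to be small and are to be read descriptively.
- **Definition.** Reconcile the meaning of positive finding in SAP 8.6 and Protocol 7.9, so that the text on evaluation and the text on reporting can be read together.

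The cost is a short SAP edit, one table from data already collected, and a wording alignment between the two documents. The table and listing need no new visit, procedure or data item.

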8.7. Deaths

If any patient dies during the study, all relevant information will be discussed in the patient narrative included in the clinical study report.

8.8. Clinical Laboratory Tests

Clinical laboratory tests (serum chemistry, hematology, coagulation, and urinalysis; see protocol Appendix M) will be performed at all visits (visit 1 [screening] through visit 5 [EOT]) using the central laboratory. All clinical laboratory test results outside of the reference range will be judged by the investigator as belonging to one of the following categories:

- abnormal and not clinically significant
- abnormal and clinically significant

A laboratory test result that is judged by the investigator as clinically significant will be recorded on the source documentation and the CRF as an adverse event, and monitored as described in Section 7.1.2 of the protocol.

Laboratory test results will be presented in standard international (SI) units in summaries. Laboratory values and changes from baseline to each visit and Last Assessment will be summarized using descriptive statistics. Shifts (below [low], within [normal], and above [high] the normal range) from baseline to each postbaseline visit and the Last Assessment will be summarized using patient counts. Baseline is defined as the last observed data before the administration of the first dose of the IMP (also see Section 4.2).

The potentially clinically significant abnormal values will be derived using criteria specified in [Table 2](#) based on all postbaseline values (including scheduled, unscheduled, and withdrawal visits). The overall incidence of potentially clinically significant abnormal values will be summarized for laboratory variables using descriptive statistics by treatment group. Listings for patients who have potentially clinically significant abnormal laboratory data will be presented.

Table 2: Criteria for Potentially Clinically Significant Laboratory Values

Test	Criterion value
Serum chemistry	
ALT	≥3x ULN
AST	≥3x ULN
ALP	≥3x ULN
GGT	≥3x ULN
LDH	≥3x ULN
BUN	≥10.71 mmol/L
Creatinine	≥177 μmol/L
Bilirubin (total)	≥34.2 μmol/L
Hematology	
Hematocrit	Men <0.37 L/L
	Women <0.32 L/L
Hemoglobin	Men ≤115 g/L
	Women ≤95 g/L
WBC counts	≤3 x 10 ⁹ /L ≥20 x 10 ⁹ /L
Eosinophils	≥10%
ANC	≤1 x 10 ⁹ /L
Platelet counts	≤75 x 10 ⁹ /L ≥700 x 10 ⁹ /L
Urinalysis	
HGB	≥2 unit increase from baseline
Glucose	≥2 unit increase from baseline
Ketones	≥2 unit increase from baseline
Total protein	≥2 unit increase from baseline

ALP=alkaline phosphatase; ALT=alanine aminotransferase; ANC=absolute neutrophil count AST=aspartate aminotransferase; BUN=blood urea nitrogen; GGT=gamma- glutamyl transpeptidase; HGB=hemoglobin; LDH=lactate dehydrogenase; RBC=red blood cell; ULN=upper limit of normal range; WBC=white blood cell

Serum beta-human chorionic gonadotropin (β-HCG) tests will be performed for all women of childbearing potential at visits 1 and 5. Urine β-HCG tests will be performed for women of childbearing potential at visits 2 through 4. Pregnancy test results will be listed.

Current menstruating status (yes or no) will be collected at all visits and listed.

8.8.1. Laboratory Values Meeting Hy’s Law Criteria

All occurrences of possible drug-induced liver injury that meet Hy’s law criteria as defined in the Section 7.1.5.1 of the study protocol will be included in serious adverse events reporting.

8.9. Physical Examinations

Physical examinations will be performed at visits 1, 2, and 5. Any physical examination finding that is judged by the investigator as a clinically significant change (worsening) compared with a baseline value will be considered an adverse event, recorded on the CRF, and monitored as described in Section 7.1.2 of the study protocol.

Abnormal physical examination findings will be listed.

Weight and height will be summarized and listed with vital signs data.

8.10. Vital Signs

Vital signs (pulse, systolic and diastolic blood pressure, and body temperature) will be measured at each (visit 1 through 5). Weight will be measured at visits 1, 2, and 5. Any vital sign value that is judged by the investigator as a clinically significant change (worsening) from a baseline value will be considered an adverse event, recorded on the source documentation and transcribed onto the CRF, and monitored as described in Section 7.1.2 of the protocol.

Vital signs (including weight) values and changes from baseline to each visit and the Last Assessment will be summarized using descriptive statistics. The incidence of potentially clinically significant abnormal values will be summarized for selected vital signs using descriptive statistics. Baseline is defined as the last observed data before the administration of the first dose of the IMP (also see Section 4.2).

Table 3 specifies the criteria for identifying vital signs as potentially clinically significant abnormal values. Note that in order to qualify as potentially clinically significant abnormal, a value needs to meet both criteria below: ie, have a value beyond the criterion value and a change of at least the magnitude specified in the change relative to baseline column. The potentially clinically significant abnormal vital signs values will include all postbaseline values (including scheduled, unscheduled, and early withdrawal visits) for the summaries.

Table 3: Criteria for Potentially Clinically Significant Vital Signs

Vital Sign	Criterion value	Change relative to baseline
Pulse	≥120 bpm	Increase of ≥15 bpm
	≤50 bpm	Decrease of ≥15 bpm
Systolic blood pressure	≥180 mm Hg	Increase of ≥20 mm Hg
	≤90 mm Hg	Decrease of ≥20 mm Hg
Diastolic blood pressure	≥105 mm Hg	Increase of ≥15 mm Hg
	≤50 mm Hg	Decrease of ≥15 mm Hg
Temperature	≥38.3°C	Change of ≥1.1°C

bpm=beats per minute

Height will be measured at screening visit, and data will be listed in the vital sign listing.

8.11. Electrocardiography

Triplicate 12-lead ECGs will be collected at visits 1, 2, and 5. Any ECG finding that is judged by the investigator as a potentially clinically significant change (worsening) compared with a baseline value will be considered an adverse event, recorded on the source documentation and in the CRF, and monitored as described in Section 7.1.2 of the protocol.

For ECG variables, the mean of recorded results from the 3 measurements at a visit will be calculated. The mean results and mean changes from baseline to EOT and Last Assessment will be summarized using descriptive statistics. Baseline is determined based on the last set of observed data before the administration of the first dose of the IMP (also see Section 4.2).

For ECG findings, the worst value of recorded findings at a visit will be used for analysis. Baseline ECG findings and shifts (normal, abnormal not clinically significant, and abnormal clinically significant) from baseline to overall (worst value for a patient) and the Last Assessment (worst value of recorded findings from the last visit) will be summarized using patient counts.

8.12. Concomitant Medications or Therapies

Concomitant medications, treatments, or procedures will be collected up to the end of study.

All concomitant medications will be coded using the WHO Drug. The incidence of concomitant medications will be summarized using descriptive statistics by therapeutic class and preferred term. Patients are counted only once in each therapeutic class category, and only once in each preferred term category. The concomitant medications will include all medications taken after administration of the first IMP.

The subset of medications or therapies will be summarized by the indication categories as indicated in Section 5.5.

9. TOLERABILITY VARIABLES AND ANALYSIS

Tolerability was not specifically defined for this study.

10. PHARMACOKINETIC ANALYSIS

There are no prespecified pharmacokinetic endpoints.

Fremanezumab plasma concentration will be summarized using descriptive statistics at each planned sampling time point for each of the active treatment groups (samples from patients who received placebo will not be analyzed). The summary will be based on the safety analysis set. The plasma concentration will be listed by active treatments, scheduled visits and time points.

11. PHARMACOGENOMIC ANALYSIS

Pharmacogenomic analysis results will be summarized for each gene tested. An attempt will be made to correlate clinical observations (pharmacokinetics, safety, efficacy, or other effects) with the genotypes observed. Additional pharmacogenomic analysis may be conducted at a later time and will be reported in a separate addendum report.

This analysis is not included in this SAP.

12. BIOMARKER ANALYSIS

Biomarker analysis will include logistic regression, receiver operating characteristic curves, and summary statistics. Results will be reported separately. Measurements will be made using validated assays.

This analysis is not included in this SAP.

13. IMMUNOGENICITY ANALYSIS

A summary of immunogenicity results will be provided, and the incidence of immunogenicity will be calculated. The impact of immunogenicity on the pharmacokinetics profile, IMP efficacy, and clinical safety will be evaluated. This ADA impact analysis will be reported separately.

This analysis is not included in this SAP.

**14. ANCILLARY STUDY ANALYSIS – WEARABLE SENSOR
SUBSTUDY**

A subset of patients (n=45, approximately 15 patients from each treatment group) from each pivotal study (TV48125-30056 and TV48125-30057), approximately 90 patients in total, will be asked to wear a sensor monitoring system (digital wearable device) on the wrist to track sleep patterns and activity patterns. These patients will be allowed to continue in the substudy during the long-term safety study (TV48124-30058).

Analyses for endpoints from the wearable sensor substudy will include summary statistics and multimodal the algorithms to monitor physiological activity, sleep/wake activity, and treatment responses. Results will be reported separately.

These analyses will include data from both pivotal studies and the long-term safety study and are not included in this SAP. A separate analysis plan will be provided.

